	2 IMRT
	3 SBRT (stereotactic body radiotherapy)
If palliative Radiotherapy, site	1 Bone lesions

	2 Nodal lesions
	3 Visceral metastases
	4 Pelvic lesions
	5 Others
Dose/fraction	__ __ , __ __ Gy
Total dose	__ __ , __ __ Gy
Association with Hormonal Therapy	
 1 Radiotherapy alone 2 Radiotherapy and neoadjuvant Hormonal Therapy (before RT) 3 Radiotherapy and adjuvant Hormonal Therapy (after RT) 4 Radiotherapy and neoadjuvant + adjuvant Hormonal Therapy
2 Brachytherapy	
Type of brachytherapy	
 1 LDR (internal radiation therapy) 2 HDR
Aim of brachytherapy	
 1 Exclusive 2 Other, specify_____
3 Radiometabolic Therapy	
If yes	
 1 With alfa-emittent particles 2 Other, specify _____
4 Hormonal Therapy	
Type of Hormonal Therapy	
 1 ADT 2 Antiandrogen

If antiandrogen, specify the type:

- 1 Ciproterone acetate
- 2 Bicalutamide
- 3 Flutamide
- 4 Other, specify _____

If antiandrogen, specify the dose:

- 3 LHRH-Agonist (or GnRH)
- 4 LHRH-Antagonist (or GnRH)
- 5 Other, specify _____

The used drugs _____

5 Focal Therapy

Type of Focal Therapy	1 High Intensity Focused Ultrasound
	2 Cryotherapy
	3 Other, specify _____

Aim of Focal Therapy	1 Curative
	2 Palliative
	3 Other, specify _____

6 Chemotherapy

Type of drug	_____
--------------	-------

Treatment scheme

7 Second line Hormonal Therapy

Type of drug	_____
--------------	-------

Treatment scheme

Has he planned further treatments related to prostate cancer, subsequent to those reported in Attachment 1 (1-month follow up)?
	
0 No
 
1 Yes, specify: If yes:
 
1 Surgery
 
2 External Beam Radiation Therapy
 
3 Brachytherapy
 
4 Radiometabolic Therapy
 
5 Hormonal Therapy
 
6 Focal Therapy
 
7 Chemotherapy
 
8 Others, specify _____

If he does not have undergone further treatments, is he able to remember the last PSA value?
	
1 Yes If yes: PSA _____ ng/mL Date of the PSA value test _____ / _____ / _____ day month year
 
0 No If no: Does he agree to ask it to his family doctor? 0 No 1 Yes What is his family doctor's name? _____
 
PSA referred by the family doctor _____ ng/mL Date of the PSA value test referred by the family doctor _____ / _____ / _____ day month year

References


Acute Toxicities

Rectal Acute Toxicity (Grade)		Date Tox.	
Urinary Acute Toxicity (Grade)		Date Tox.	
Small Intestine Acute Toxicity (Grade)		Date Tox.	

GI Acute Toxicity (small bowel)

(see Table 1)

select (1=G0, 2=G1, 3=G2, 4=G3, 5=G4, 6=Unknown)

Date yyyy-mm-dd

Rectal Acute Toxicity

select (1=G0, 2=G1, 3=G2, 4=G3, 5=G4, 6=Unknown)

Date yyyy-mm-dd

Urinary Acute Toxicity

select (1=G0, 2=G1, 3=G2, 4=G3, 5=G4, 6=Unknown)

Date

Late Toxicity bladder/ rectum

select (1=Yes, 2=No, 3=Unknown)

Date yyyy-mm-dd

Proctitis

select (1=G0, 2=G1, 3=G2, 4=G3, 5=G4, 6=I Unknown)

Date yyyy-mm-dd

Cystitis

select (1=G0, 2=G1, 3=G2, 4=G3, 5=G4, 6= Unknown)

Date yyyy-mm-dd

Impotence

select (1=No, 2=Yes pre RT, 3=Yes post RT, 4= Unknown)

Date yyyy-mm-dd

Incontinence

select (1=No, 2=Yes pre RT, 3=Yes post RT, 4=Unknown)

TABLE 1 – Toxicity

RECTAL/SMALL BOWEL Acute TOX

G0: No Toxicity

G1: Increased alvus frequency not requiring any treatment. Rectal pain or abdominal pain not requiring any painkillers

G2: Diarrhoea, mucositis, rectal pain or abdominal pain requiring painkillers

G3: Diarrhoea requiring parenteral supportive care, severe mucositis or haematological alterations requiring treatment. Abdominal distension

G4: Acute or subacute obstruction, fistula or perforation, haemorrhage requiring blood transfusion. Abdominal pain or tenesmus requiring ileostomy

BLADDER Acute TOX

G0: No Toxicity

G1: Low urinary tract symptoms (LUTS) and dysuria not requiring any treatment

G2: LUTS, dysuria and urgency requiring treatment or anaesthetics

G3: Severe LUTS, urgency, dysuria, pelvic pain or bladder spasms and haematuria

G4: Haematuria requiring blood transfusion, urinary obstruction, ulceration and necrosis

Late TOX PROCTITIS

G0: No Toxicity

G1: Mild rectal pain, Slight diarrhoea (less than 5 discharges). Small bleeding

G2: Diarrhoea (more than 5 discharges). Significant mucosal secretions and intermittent rectal bleeding

G3: Obstruction or haemorrhage requiring surgery

G4: Necrosis, perforation or fistula

Late TOX CYSTITIS

G0: No Toxicity

G1: Slight epithelial atrophy, small telangiectasia, microscopic haematuria

G2: Moderate LUTS, Intermittent macroscopic haematuria

G3: Severe LUTS and dysuria spread of telangiectasia. Frequent haematuria. Reduction in bladder capacity (less than 150 cc)

G4: Necrosis, bladder capacity reduced (less than 100 cc). Severe haemorrhagic cystitis

SF-12 STANDARD ITALIAN VERSION

(Apolone G et al. 2001)

	Excellent	Very good	Good	Fair	Poor
1 In general, you would say that your health condition is:	1	2	3	4	5
The following questions regard some activities you might do during a typical day. Does your health condition actually limit you in doing these activities?					
	Yes, it limits a lot	Yes, it limits a little	No, it does not limit at all		
2 Activities of moderate physical effort , such as moving a table , using the vacuum cleaner , playing bowls or a riding a bicycle	1	2	3		
3 Climbing several flights of stairs	1	2	3		
During the last 4 weeks have you had the following problems at work or during other daily activities, because of your physical health condition?					
	Yes	No			
4 Accomplished less than you would like	1	2			
5 You had to limit certain kinds of occupation or other activities	1	2			
During the last 4 weeks have you had the following problems at work or during other daily activities, because of your emotional state (such as feeling depressed or anxious)?					
	Yes	No			
6 Accomplished less than you would like	1	2			
7 You did not do work or other activities as carefully as usual	1	2			
	Not at all	A little bit	Moderately	Quite a bit	Not at all
8 During the last 4 weeks , How much has pain hindered your usual work (at home and outside)?	1	2	3	4	5
How long during the last 4 weeks have you felt					
	All of the time	Most of the time	A good bit of time	Some of the time	A little of the time
9 calm and serene?	1	2	3	4	5
10 full of energy?	1	2	3	4	5
11 discouraged and sad	1	2	3	4	5
	All of the time	Most of the time	A good bit of time	Some of the time	A little of the time
12 During the last 4 weeks , how long have your physical health condition or your emotional state interfered with your social activities, with family, with friends?	1	2	3	4	5

COMPLICATIONS DUE TO PROSTATE CANCER
ITALIAN UCLA PROSTATE CANCER INDEX
(Gacci M et al, 2005)

URINARY FUNCTION

This session regards the urinary routine. Please consider only the last 4 weeks.

1. Over the LAST 4 WEEKS, how often have you leaked urine?
 - 1 Every day.
 - 2 About once a week
 - 3 Less than once a week
 - 4 Not at all.
2. Which of the following best describes your urinary control during the LAST 4 WEEKS?
 - 1 No control whatsoever
 - 2 Frequent dribbling
 - 3 Occasional dribbling
 - 4 Total control
3. How many pads or adult diapers per day have you usually used to control leakage during the LAST 4 WEEKS?
 - 1 3 or more pads per day
 - 2 1-2 pads per day
 - 3 No pads
4. How big a problem, if any, has each of the following been for you?
Dripping urine or wetting your pants?
 - 0 No problem
 - 1 Very small problem
 - 2 Small problem
 - 3 Moderate problem
 - 4 Big problem
Urine leakage interfering with your sexual activity?
 - 0 No problem
 - 1 Very small problem
 - 2 Small problem
 - 3 Moderate problem
 - 4 Big problem
5. Overall, how big a problem has your urinary function been for you during the LAST 4 WEEKS?
 - 0 No problem
 - 1 Very small problem
 - 2 Small problem
 - 3 Moderate problem
 - 4 Big problem

BOWEL FUNCTION

The following section talks about all the bowel function and abdominal pain. Please consider only the last 4 weeks.

6. How often have you had rectal urgency (felt like you had to pass stool, but did not) during the LAST 4 WEEKS?
 - 1 More than once a day
 - 2 About once a day
 - 3 More than once a week
 - 4 About once a week
 - 5 Rarely or never
7. How much distress have your bowel movements caused you during the LAST 4 WEEKS?
 - 1 Severe distress

2 Moderate distress
 3 A little distress
 4 No distress

8. How often have you had crampy pain in your abdomen or pelvis during the LAST 4 WEEKS?
 1 Several times a day
 2 About once a day
 3 Several times a week
 4 About once this month
 5 Rarely or never

9. In particular, how big was the problem of bowel habits during the LAST 4 WEEKS?
 1 Big problem
 2 Moderate problem
 3 Little problem
 4 Very small problem
 5 No problem

SEXUAL FUNCTION

THE NEXT SECTION IS ABOUT YOUR SEXUAL FUNCTION AND SEXUAL SATISFACTION. MANY OF THE QUESTIONS ARE VERY PERSONAL, BUT THEY WILL HELP US UNDERSTAND THE IMPORTANT ISSUES THAT YOU FACE EVERY DAY. REMEMBER THAT YOUR ANSWERS TO THIS QUESTIONNAIRE WILL BE KEPT CONFIDENTIAL AND WILL BE USED ONLY FOR RESEARCH PURPOSES. PLEASE ANSWER HONESTLY ABOUT THE LAST 4 WEEKS ONLY.

10. HOW WOULD YOU RATE EACH OF THE FOLLOWING DURING THE LAST 4 WEEKS?

	Very poor	Poor	Fair	Good	Very good
A. Your ability to have an erection?.	1	2	3	4	5
B. Your ability to reach orgasm (climax)	1	2	3	4	5

11. How would you describe the usual QUALITY of your erections?
 1 None at all
 2 Not firm enough for any sexual activity
 3 Firm enough for masturbation and foreplay only
 4 Firm enough for intercourse

12. How would you describe the FREQUENCY of your erections?
 1 I NEVER had an erection when I wanted one
 2 I had an erection LESS THAN HALF the time I wanted one
 3 I had an erection ABOUT HALF the time I wanted one
 4 I had an erection MORE THAN HALF the time I wanted one
 5 I had an erection WHENEVER I wanted one

13. Overall, how would you rate your sexual function during the LAST 4 WEEKS?
 1 Very poor
 2 Poor
 3 Fair
 4 Good
 5 Very good

14. Overall, how big a problem has your sexual function been for you during the LAST 4 WEEKS?
 1 No problem
 2 Very small problem
 3 Small problem
 4 Moderate problem
 5 Big problem

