In summary, the study aims at the definition of survival, toxicity and QoL data in a representative sample of intermediate, high and very high risk prostate cancer patients consecutively recruited in Italian Radiation Oncology Centres over two years. Parameters considered will be OS, CSS and bRFS, toxicity (rectal, bladder, bowel toxicity, according to CTCAE v.4 scale) and QoL (according to the SF-12 scale and UCLA-PCI scale). Primary end point will be OS. Secondary endpoints will be CSS, bRFS, gastrointestinal and genitourinary toxicity, QoL deterioration.

Study Design

This is a prospective, multicenter, observational cohort study aimed to describe the advantage/disadvantage of different treatments of patients with intermediate/high/very high risk prostate cancer, through a web-based database.

Study Duration

The recruitment period, taking into account the needed sample size (*v.infra*) will be of two years, followed by three-year follow up period for each patient, with an accrual of at least 400-500 patients.

Population, Procedures

The study will include all consecutive patients affected by intermediate, high or very high-risk prostate cancer that fit the inclusion criteria and who are evaluated at each Centre involved in the study. Patients may have already undergone or not to radical prostatectomy and/or pelvic lymphadenectomy.

Inclusion criteria

- Men older than or aged 18 years;
- Histologically confirmed intermediate, high or very high risk prostate cancer patients (NCCN classification: Intermediate Risk T2b and T2c or Gleason Score 7 or PSA value between 10 and 20 ng/mL; High risk: T3a or Gleason score 8-10 or PSA > 20 ng/ml; Very high risk: T3b-T4 or patients with multiple adverse risk factors reported in the high risk category that may be shifted in the very high risk group
- Patients eligible for -and actually submitted to- radical radiotherapy treatment (+/- androgen deprivation) or adjuvant radiotherapy treatment after surgery (radical prostatectomy +/- pelvic lymphadenectomy);
- No other synchronous or previous malignant tumor other than skin basal cell carcinoma;
- Patients able to understand and sign the appropriate informed consent;
- Patients able to fill the QoL questionnaire;

Exclusion criteria

- Patients aged less than 18;

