- Treatment : type of treatment, start date, PSA value before treatment; if surgery type of surgery and pathological TNM, margins, Gleason Score, number of positive lymph nodes; if external RT (intent, modality, technique, dose/fraction, volumes, concomitant hormonal therapies); if brachytherapy (type, intent, dose); if hormone therapy (type of drugs, start and end date, total duration);
- Acute and late toxicities;
- Biochemical Relapse with PSA value and date of last PSA;
- Quality of life and symptoms due to prostate cancer (Italian UCLA-PCI);
- General quality of life SF-12.

Toxicity and response evaluation

The enrolled patients will undergo the first follow up visit one month after the end of radiotherapy. On that occasion, clinical examination will be performed and previously prescribed blood tests, if required, will be evaluated. Genitourinary and gastrointestinal toxicity due to radiation therapy for prostate cancer will be reported according to the NCI Common Terminology Criteria for Adverse Events (CTCAE) version 4 for adverse event (AE) reporting. The CTCAE version 4 is identified and located on the CTEP web site at:

http://ctep.cancer.gov/protocolDevelopment/electronic_applications/ctc.htm [48]

In addition, a Case Report Form (CRF) will be completed (see Attachment 2), regarding:

- Technical characteristics of the radiation treatment (dose, volume, technique, association or not with hormonal therapy);
- Quality of life and complications due to prostate cancer (according to Italian UCLA-PCI) [45, 46];
- General quality of life (SF-12 Standard V1) [47].

Thereafter patients will be evaluated at 3-months, 6-months and 12-months after the end of radiotherapy, and then every 6 months for at least 24 months. During all those scheduled follow up visits, PSA level (jointly with testosterone, in case of association with hormonal therapy) and

previously prescribed blood texts if required, will be evaluated. Patients will undergo clinical examination, and genitourinary and gastrointestinal toxicity will be assessed according to the CTCAE v4.0 classification scale). In addition, a CRF (see Attachment 3) will be completed at each visit, regarding:

- Survival status (mortality, date and cause of death) or exit from the study;
- If macroscopical recurrence or disease progression occurred, the radiological exams (if performed);
- Further treatments received/planned after radiotherapy;
- The last available PSA;

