ATTACHMENT 3 – 3, 6, 9, 12, 18, 24, 36 MONTHS FOLLOW UP

	
1 He does not adhere anymore for health reasons, specify _____
 
2 He is not interested anymore to take part in the study
 
3 He is not traceable

Does the patient still undergo Hormonal Therapy?	
1. Yes
 
If yes: (FILL IN POINT 4 BELOW)
 
0 No
 
If no: Date of ending hormonal therapy  / /  day month year

Has he developed new comorbidities? (It is possible to fill in more than one option)	
0 . No
 
1 . Yes
 
If yes:
 
 1 Cardiac (specify _____) 2 Vascular (including hypertension) 3 Pulmonary (specify _____) 4 Eye, ear, nose, throat, larynx 5 Gastro-intestinal (specify _____) 6 Hepatic (liver only) 7 Renal (kidneys only) 8 Musculo-skeletal (specify _____) 9 Intertegumentary (skin) 10 Neurological (specify _____) 11 Endocrine-metabolic (specify _____) 12 Cognitive-psychiatric, behaviour 13 Genito-urinary (ureter-genitals) (specify _____) 14 Other malignancies (including Haematopoietic malignancies)

	15 Other, specify _____	
Has he undergone further treatments for prostate cancer, subsequent to those reported in Attachment 1 (1-month follow up)?	0 No	
	1 Yes	
	If yes:	
	1	Surgery
	2	External Beam Radiation Therapy
	3	Brachytherapy
	4	Radiometabolic Therapy
	5	Hormonal Therapy
	6	Focal Therapy
7	Chemotherapy	
8	Others, specify _____	

If he has undergone further treatments, specify:

Date of starting the new treatment |__|/|__|/|__|_|_|

day month year

PSA before starting the new treatment |__|_|_|_|. |__|_|_| ng/mL

 External Beam Radiotherapy	
Aim of Radiotherapy	1 Palliative
	2 Other, specify_____
Modality	1 IGRT
	2 Non IGRT
Technique	1 3D-CRT

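### The visible last-PSA item in Attachment 3 relies on recall and depends on later treatment, in conflict with the PSA the protocol schedules at every follow-up visit

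*Combined protocol and SAP*

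**What the plan says.** The section headed Toxicity and response evaluation sets out follow-up after the one-month visit. The sentence on PSA begins "During all those scheduled follow up visits, PSA level (jointly with testosterone, in case of association with hormonal therapy" and goes on to say that these are evaluated. The same paragraph states that "a CRF (see Attachment 3) will be completed at each visit, regarding" a list of contents, one of which is "The last available PSA". Nothing there limits the item to some patients or mentions recall. The CRF contents listed under Phase 3: Follow-up also include "Biochemical Relapse with PSA value and date of last PSA".

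Attachment 3 as printed has two routes to a PSA value:

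- **No further treatment.** The form asks: "If he does not have undergone further treatments, is he able to remember the last PSA value". If yes, value and test date are entered. If no, the next question is "Does he agree to ask it to his family doctor"; if he agrees, the doctor's value and date are entered. If he does not agree, there is no field to fill.
- **Further treatment.** The form records the start date of that treatment and "PSA before starting the new treatment". It prints no date for that test and no later PSA.

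The endpoint served by these data is named in the summary of the study: "Secondary endpoints will be CSS, bRFS, gastrointestinal and genitourinary toxicity, QoL deterioration".

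**The concern.** bRFS is a time-to-event endpoint built on PSA. It needs dated values from a known source, collected in the same way from every patient. The protocol body provides for that, since the test is evaluated at the visit. The printed form does not carry it through: at a visit where a PSA result is evaluated, it asks the patient what he remembers.

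Three things can go wrong if the form is followed literally:

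- A recalled value or date can be wrong, so that a relapse is missed or misplaced in time.
- A man who neither remembers nor agrees to contact with his doctor contributes no value at that visit.
- The route depends on later treatment, which may itself follow a relapse. In that branch the PSA is undated, so a relapse seen only there could be dated only from the start of the new treatment.

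bRFS also enters the first and third open questions in the rationale, and the fifth aim compares outcomes with historical AIRO data. A weakness in how PSA is captured would reach those comparisons.

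**Working it through.** **1. Body and form side by side**

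| Feature | Protocol body | Attachment 3 as printed |
|---|---|---|
| When PSA is obtained | Every scheduled follow-up visit | No visible field for the PSA of that visit |
| Who gives a last PSA | All patients, no condition | Recall item only for men without further treatment |
| Source | PSA evaluated at the visit | Memory, then family doctor if the patient agrees |
| Date of test | Listed with biochemical relapse | Present in the recall and family-doctor fields; absent for the PSA before a new treatment |
| Priority between sources | Not stated | Memory is asked first; laboratory result not mentioned |

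**2. Is the recall item the form's version of the last available PSA?** The body lists the form's contents as survival status or exit, recurrence imaging, further treatments received or planned, last PSA, then quality of life. The visible form runs from exit reasons through further treatments received and planned to the recall item, and later to the questionnaires. The recall item stands where the list puts the last PSA, so it is most likely that field. This is a reading of the layout, not a statement in the documents.

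**3. The plan's only precision figure.** It concerns 5-year overall survival, with N = 400 and S = 0.8: 0.8 ± 1.96 × √(0.8 × 0.2 / 400) = 0.8 ± 0.0392, or 0.761 to 0.839. This reproduces the stated 0.76 to 0.84. PSA does not enter it. No such figure is given for bRFS.

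**4. Illustration of what PSA loss could do to bRFS.** All inputs are assumed: N = 400, true relapse-free proportion S = 0.80, simple proportions without censoring. Let r be the share of relapsed men without usable PSA and f the share of relapse-free men without it. The complete-case estimate is S(1 − f) / [S(1 − f) + (1 − S)(1 − r)].

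- r = f = 0.30: 0.56 / (0.56 + 0.14) = 0.80. There is no bias. N falls to 280 and the half-width is 1.96 × √(0.16 / 280) = 0.047.
- r = 0.30, f = 0.10: 0.72 / (0.72 + 0.14) = 0.837.
- r = 0.50, f = 0.10: 0.72 / (0.72 + 0.10) = 0.878.
- r = 0.10, f = 0.30: 0.56 / (0.56 + 0.18) = 0.757.

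With S = 0.70, the 30%/10% and 50%/10% cases give 0.750 and 0.808; with S = 0.90 they give 0.920 and 0.942. If missing PSA is instead counted as no relapse, S = 0.80 becomes 1 − 0.20 × 0.70 = 0.86 with r = 0.30, and 1 − 0.20 × 0.50 = 0.90 with r = 0.50.

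Equal loss costs precision only. Loss concentrated in relapsed men pushes bRFS up, and loss concentrated in relapse-free men pushes the complete-case estimate down. The documents fix neither r nor f, nor how missing PSA is handled, so both direction and size come from the assumptions.

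**The case against.** The strongest objection is that the form is incomplete in the copy reviewed. Attachment 3 opens in the middle of an item, with reasons for leaving the study and no question above them. The survival and recurrence-imaging rows promised in the body are not visible either. The references printed after the recall item include a paper on defining biochemical failure after radiotherapy and works on relapsing and castration-resistant disease, yet no visible item cites them. In Attachment 1, by contrast, the footnote belongs to a marked item. A biochemical-failure item may well have existed. This stands: the absence of such a field must not be asserted. It does not rescue the recall item. If a laboratory field exists elsewhere, the form has two PSA sources and no rule for which prevails.

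Second, men with further treatment are not left without PSA. They have a dedicated field for the value before the new treatment, and for a first biochemical relapse that is the informative one. This also stands, and it narrows the gap in that branch to the missing test date.

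Third, recall is not the only source. The family-doctor fallback carries a date, and the form is repeated over several visits, so one missed value may delay detection of a relapse without erasing it. That is fair, but delayed detection is itself an error in a time-to-event endpoint, and the fallback depends on the patient's agreement.

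**Conclusion.** The point holds as a conflict between the protocol body and the printed follow-up form. The body schedules PSA at each visit and promises an unconditional last value; the visible item is conditional on no further treatment, asks for memory first and gives the laboratory result no priority. Followed as printed, it can miss or misdate relapses.

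The size cannot be derived from the documents. Overall survival and the calculation for 400 patients are unaffected, so this is a data-quality correction for a secondary endpoint and no threat to the main design.

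Two stronger readings are tempting. A reader might infer that bRFS will rest on recalled values whose absence depends on the outcome. The documents do not show this: the CRF contents include biochemical relapse with PSA value and date, part of the form is not visible, and treated men have their own PSA field. A reader might also attach a figure by multiplying a relapse proportion by a share missed, for example 0.15 × 0.10 = 1.5 points up to 0.25 × 0.30 = 7.5 points of overstatement. Neither input is in the documents. The product counts every missed relapse as relapse-free, ignores loss among relapse-free men, and applies the share to treated relapses that bypass the recall item.

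**What to change.** First check the complete Attachment 3 for a laboratory PSA or biochemical relapse field. Whatever it shows, make three changes:

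- Replace the recall item with PSA value, sample date and source (laboratory report, family doctor, patient report) at every visit, for all patients whether or not they had further treatment. State that the laboratory result takes priority and that recall is a flagged last resort. If another PSA field exists, merge the two or state which prevails.
- Add a test date to the PSA recorded before a new treatment.
- Add to the statistical section a bRFS sensitivity analysis that excludes recalled values.

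The cost is a few form and database fields, slightly more data entry and one extra analysis. The PSA evaluation is already scheduled, so no procedure is added. How biochemical relapse is defined is a separate matter that this change does not settle.
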